7.3.4.3 Accidental Food Allergen Exposure

An accidental food allergen exposure is any known or suspected exposure to a food to which the subject is allergic, including peanut, whether or not it results in an AE.

To report the occurrence of a safety event associated with accidental food ingestion, subjects will be instructed to contact the site study coordinator or Investigator after any known or suspected food allergen exposure, even if it does not cause symptoms. The subject may be asked to return to the site. These events will be reported as follows:

- The non-serious AEI form will be completed for each of these events, in addition to events where consumption of peanut without a reaction occurs, *unless*:
- The accidental food ingestion safety event meets the definition of an SAE, as defined in Section 7.3.3), in which case the AE form will be completed.

If an accidental food allergen exposure does not result in an AE, no assessment of severity, seriousness, or relatedness is required.

7.3.4.4 Adverse Event Featuring a Severe Symptom

The severity of symptoms will be determined on the basis of the Investigator's judgment. Severity definitions for allergic reactions to IP were developed to be consistent both with the PRACTALL consensus report and with the CoFAR grading system and are provided in Section 6.5.1 and the table in Appendix 5 as a general guide. Severe allergic AEs may include:

- Skin – severe generalized urticaria/angioedema/erythema;
- Respiratory – laryngeal edema, throat tightness with hoarseness, wheezing with dyspnea, stridor;
- GI – severe abdominal pain/cramping/repetitive vomiting and/or diarrhea;
- Neurological – change in mental status;
- Circulatory – clinically significant hypotension.

Severity of other AEs will be assigned using other grading systems as discussed in Section 7.4.

7.3.4.5 Adverse Events Associated with Use of Epinephrine

AEs may result in epinephrine use. Upon awareness of such an event, site staff will report it within 24 hours using the AEI form, independent of severity or relatedness, or whether it was administered in the CRC or at home. If the epinephrine was used as part of an allergic reaction that meets criteria for anaphylaxis, an accidental food allergen exposure, an AE featuring a

severe symptom, or an SAE, the use need not be reported separately. The intent of this AEI is to capture events that may be occurring that do not fall into one of these other categories.

7.4 Severity Grading

The Investigator is to assign severity grades to AEs. Depending on the type of AE, different severity grading systems will be used in this study.

- The severity grading of allergic reactions will be according to the definitions developed by the CoFAR group ([Appendix 5](#)).
- The severity of anaphylactic reactions will be graded according to the EAACI system for grading the severity of anaphylactic reactions ([Appendix 4](#)).
- For grading the severity of all other AEs, the National Cancer Institute's Common Terminology Criteria for Adverse Events (NCI-CTCAE) system will be used. The purpose of using the NCI-CTCAE system is to provide standard language to describe AEs (toxicities) and to facilitate tabulation and analysis of the data and for assessment of the clinical significance of treatment-related toxicities. The NCI-CTCAE provides a term and a grade that closely describes the AE. Each participating site will receive copies of the grading scales and event descriptions.

For AEs not included in the NCI-CTCAE listing, they are also to be graded on a scale from 1 to 5, according to the definition provided below:

Grade 1	Mild	Transient or mild discomforts (< 48 hours), no or minimal medical intervention/therapy required, hospitalization not necessary (non-prescription or single-use prescription therapy may be employed to relieve symptoms, (eg, aspirin for simple headache, acetaminophen for post-surgical pain)
Grade 2	Moderate	Mild to moderate limitation in activity, some assistance may be needed; no or minimal intervention/therapy required, hospitalization possible
Grade 3	Severe	Marked limitation in activity, some assistance usually required; medical intervention/therapy required, hospitalization possible
Grade 4	Life-threatening	Extreme limitation in activity, significant assistance required; significant medical/therapy intervention required, hospitalization, or hospice care probable
Grade 5	Death	Death

For additional information and a printable version of the NCI-CTCAE v. 4.03 manual, consult the NCI-CTCAE website, <http://ctep.cancer.gov/reporting/ctc.html>.

7.4.1 Guidelines for Determining Causality of an Adverse Event

The Investigator will use the following question when assessing causality of an AE to IP: Is there a reasonable possibility that the IP caused the event?

An affirmative answer designates the event as a suspected adverse reaction.

7.5 Data Safety Monitoring Committee

Although the safety of peanut OIT overall is well established, a DSMC will monitor the study for safety. The DSMC will meet periodically to review accruing safety data. The committee will consist of individuals with extensive multicenter clinical study experience drawn from the fields of clinical immunology (specifically food allergies) and biostatistics. These individuals will be entirely independent of the conduct of the study. Further details will be provided in the DSMC Charter.

7.6 Adverse Event Collection Procedures

Any new event or experience that was not present at Screening, or worsening of an event present at Screening, is considered to be an AE. Unchanged, chronic conditions are not AEs and should not be recorded on the AE page of the CRF. AEs will be evaluated from the onset of the event until the time the event is resolved or medically stable, or until 30 days after the Exit or Early Discontinuation Visit, whichever comes first. AEs ongoing at the time that study treatment is discontinued may not be determined to be medically stable until 30 days after the Exit or Early Discontinuation Visit has been conducted, in which case additional visits after the Exit or Early Discontinuation Visit may be required. For the specific case of GI-related AEIs, the need for additional follow-up is outlined in Section 7.3.4.2. Investigators should also report AEs discovered after cessation of dosing and prior to the Early Discontinuation Visit.

AEs may be discovered through any of these methods:

- Observing the subject
- Questioning the subject, which should be done in an objective manner
- Receiving an unsolicited complaint from the subject
- Review of medical records/source documents
- Review of home-dosing symptom diary (provided to record symptoms between visits)

7.6.1 Recording and Reporting Procedures

A multi-screen AE eCRF will be used allowing all AEs to be submitted through a single reporting mechanism (Figure 3). Serious AEs will require additional information reported on additional screens within the EDC system. Source documents, with subject identifiers redacted, can be scanned and attached to the AE form as well. The Investigator will treat subjects experiencing AEs appropriately and observe them at suitable intervals until their symptoms resolve or their status stabilizes.

7.6.2 Serious Adverse Event Recording and Reporting Procedures

Serious AEs will be recorded on the AE CRF. All centers are obligated to report SAEs within 24 hours of their occurrence and/or the site's knowledge of the event to the Sponsor. The following attributes will be assigned:

[figure not shown]
- Description
- Date of onset and resolution (if known when reported)
- Severity
- Assessment of relatedness to test article
- Action taken

The Investigator will apply his/her clinical judgment to determine whether an AE is of sufficient severity to require that the subject be removed from treatment. If necessary, an Investigator will suspend any trial procedures and institute the necessary medical therapy to protect a subject from any immediate danger.

Subsequent review by regulatory health authority(ies), the DSMC, IRB / EC, or the Sponsor may suspend further trial treatment or procedures at a site. The study Sponsor and the regulatory health authorities retain the authority to suspend additional enrollment and treatments for the entire study as applicable.

A subject may voluntarily withdraw from treatment due to what he/she perceives as an intolerable AE, or for any other reason. If voluntary withdrawal is requested, the subject should be asked to continue (at least limited) scheduled safety evaluations, complete a study termination form, and be given appropriate care under medical supervision until the symptoms of any AE resolve or their condition becomes stable.

Figure 3: Reporting Decisions for Adverse Events

1. Site to notify the site's Principal Investigator of event(s)
2. Site to complete and transmit an AE Form through the EDC system. Information regarding an SAE report must be recorded in the subject's medical chart
3. SAE follow-up reports should include, as applicable, hospital admittance notes, hospital discharge summary, clinical notes, resolution date, treatment, and any other pertinent information regarding the event. Reporting should not be delayed in order to provide these documents.
4. In the event of a death, the AE Form must be completed and transmitted along with other supporting data (death certificate, medical notes, etc).

7.7 Serious Adverse Event Notification

7.7.1 Notifying the Sponsor

Investigators will provide the Reporting Center (ProPharma Group, St. Paul, MN) with data of all SAEs as defined per the protocol on an ongoing basis. As noted above, the initial contact should be within 24 hours of site awareness of the event.

7.7.2 Expedited SAEs Reporting to Regulatory Health Authorities

The sponsor's Medical Monitor will review each SAE report and will determine whether the SAE must be reported to regulatory health authorities on an expedited basis. The final decision for disposition regarding expedited reporting to the regulatory health authorities rests with the sponsor's Medical Monitor. The Sponsor will provide the DSMC and the Reporting Center with copies of any expedited SAE reports submitted to regulatory health authorities.

The Reporting Center will provide these expedited reports to the individual Investigators. Events that are serious, related to therapy, and unexpected will be reported to regulatory health authorities within 15 days or for deaths and life-threatening events within 7 days (as per applicable regulatory reporting requirements).

7.7.3 Notifying the DSMC

The Reporting Center will provide the DSMC with listings of all SAEs on an ongoing basis. Furthermore, the DSMC will be informed of expedited SAE reports. Periodic reports from the DSMC as to the overall safety of the ongoing study, and recommendations regarding continuation will be sent to the Investigators for forwarding to their IRBs/ECs if requested.

Investigational sites are instructed to report episodes of anaphylaxis within 24 hours of their occurrence and/or the sites being notified of the event to the Reporting Center for expedited review by the DSMC if the event is associated with any of the following:

- An ER visit;
- Hospitalization;
- More than 2 doses of epinephrine being given as treatment for the same episode;
- Assessment of the anaphylaxis as severe, as defined in [Appendix 4](#).

An initial Anaphylaxis Episode form containing the information known to the site at the time will be transmitted to the Reporting Center. The Reporting Center will then relay to the Sponsor the individual anaphylaxis reports as they are obtained. The investigational site will supplement the initial Anaphylaxis Episode form with additional information pertaining to the event as it becomes available and will forward the information to the Reporting Center.

7.7.4 Notifying the Institutional Review Board and Ethics Committee

The Investigator will ensure the timely dissemination of all AE information, including expedited reports and DSMC safety reviews, to the IRB/EC in accordance with applicable local regulations and guidelines.

7.8 Other Safety Assessments and Precautions

7.8.1 Physical Examination and Vital Signs

Physical examinations will be conducted at visits indicated in [Appendix 1](#). Height and weight will also be recorded at specified visits. Vital signs will be measured, including BP, PR, and body temperature. Except where a complete, age-appropriate physical examination is specifically indicated, a limited physical exam may be performed.

7.8.2 Prior and Concomitant Medications

Prior and concomitant medications will be documented in the CRF.

7.8.3 Pregnancy Testing and Contraception

7.8.3.1 Pregnancy Testing

All sexually active female subjects of childbearing potential will undergo a serum pregnancy test at screening and then urine pregnancy tests at specific subsequent visits.

7.8.3.2 Contraception

Subjects undergoing OIT are at increased risk for experiencing allergic reactions and may be at increased risk for experiencing anaphylaxis. Anaphylaxis can cause a dangerous drop in BP, and if this were to occur during pregnancy, it could result in compromised placental perfusion and significant risk to the fetus.

Pregnancy is a time when the mother's immune system undergoes complex and incompletely understood changes that are believed to reduce the risk of a maternal immune reaction directed against the fetus. It is also a time when the fetus's immune system is developing. Oral immunotherapy, at its core, entails repeated stimulation of the immune system to affect changes in its makeup and function. What effects OIT-induced changes in the immune system might have on the course of pregnancy or fetal development are currently unknown. Accordingly, sexually active female subjects of childbearing potential are required to practice effective birth control for the duration of the study.

Sexually active female subjects are to use either:

- A highly effective method of birth control, defined as one that results in a low failure rate (ie, less than 1 percent per year) when used consistently and correctly, such as implants, injectables, combined oral contraceptives, some intrauterine contraceptive devices, sexual abstinence, or a vasectomized partner; or
- Alternatively, if a single highly effective method of birth control is not used, an effective, double barrier method of contraception (eg, male condom with female condom, cervical cap, diaphragm, or contraceptive sponge) may be used.

7.9 Stopping Rules

7.9.1 Overall Stopping Rules

The study will be suspended at any time if a treatment-associated death occurs in a subject receiving AR101 active therapy, or if the second of 2 subjects is admitted to the hospital within 6 months of the first as a direct consequence of dosing with AR101. Suspension of the study will entail halting the enrollment of subjects and refraining from any dose increases, but will not entail cessation of dosing unless so directed by the FDA, the applicable regulatory health authority(ies), or advised by the DSMC and agreed to by the Sponsor. The suspension will not be lifted and dose escalation will not be resumed until the information has been discussed with regulatory authorities and the regulatory authorities either concur with resumption of up-dosing or direct discontinuation of the study in their jurisdictions.

The DSMC will also be continually reviewing safety data, and can also recommend, in its judgment, halting the study for any substantial imbalance in AEs, apart from anticipated allergic dosing symptoms.

Aimmune additionally reserves the right to discontinue the study at any time for any reason. The regulatory health authority(ies) and IRBs/ECs will be notified in the event of study discontinuation.

7.9.2 Individual Stopping Rules

Individuals may stop the study at any time by withdrawing their consent if they experience subjectively intolerable AEs, dosing symptoms, or for any other reason. In addition, > 7 consecutive days of missed daily dosing due to non-compliance (ie, for any reason other than treatment of an AE or an IP dispensing error) constitutes an individual stopping rule. During Up-dosing, subjects must halt up-dosing and re-start with a reduced dose if more than 4 days of dosing are missed. Missing 3 or more consecutive days on 3 occasions is an individual stopping rule, as is missing 15 or more consecutive days of dosing for any reason, with one exception of the voluntary 4-week hiatus for GI AEIs occurring at or before the 20 mg dose, as specified in Section 6.5.3.2.

Occurrence of any of the following will result in the cessation of dosing and the subject being discontinued from the study as an escalation failure non-responder, resulting in an Early Discontinuation Visit within 14 days:

- Failure to accomplish up-dosing of IP after 3 attempts
- Failure to identify a tolerated dose of IP after 3 attempts at dose reduction

Finally, administration of 3 or more doses of epinephrine for the treatment of any dose-related allergic reaction in any subject is an individual stopping rule.

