4.3 Early Termination

4.3.1 Criteria for Early Termination

Any subject will be prematurely terminated from additional IP exposure for the following reasons:

1. Life-threatening symptoms (Consortium of Food Allergy Research [CoFAR] Grade 4; refer to the table in [Appendix 5](#)), including, but not limited to, anaphylaxis resulting in hypotension, neurological compromise, or mechanical ventilation secondary to peanut OIT dosing or any peanut food challenge
2. Severe symptoms (CoFAR Grade 3; refer to the table in [Appendix 5](#)), including, but not limited to, those that require intensive therapy (to be determined by the Investigator, but may include such interventions as intravenous (IV) epinephrine, intubation, or admission to an intensive care unit) or those that are recurrent

Any subject may be prematurely terminated from additional IP exposures for the following reasons:

1. Poor control or persistent activation of secondary atopic disease (eg, atopic dermatitis, asthma)
2. Starting any prohibited medication (Section [5.10](#)), with no alternative medications available per the prescribing doctor, unless a waiver has been obtained from the Medical Monitor, as per Section [5.7](#)
3. Pregnancy
4. Non-adherence (non-compliance) with IP dosing, as indicated by missing > 7 consecutive dosing days on any 1 occasion, or 3 consecutive dosing days on 3 or more occasions during the Up-dosing Period, as this could constitute a potential safety issue
5. Medically-indicated circumstances (eg, as part of the treatment for inter-current AEs) that require missed IP dosing for > 14 consecutive days, with the exception of the voluntary 30-day hiatus for GI-related AEs occurring at or before the 20-mg dose level

Any subject may also be prematurely discontinued from the study if:

1. The subject elects to withdraw consent from all future study activities, including follow-up.
2. The subject is lost to follow-up (ie, no further follow-up is possible because attempts to reestablish contact with the subject have failed).
3. The subject develops biopsy-documented EoE.
4. The subject's continued participation in the study is assessed by the Investigator to constitute a threat to the safety of the subject or the safe conduct of the study.
5. The subject dies.
6. The Sponsor discontinues the study.

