6.6 Missed OIT (Investigational Product) Doses during Up-dosing

Missed doses of IP at any phase of the study can pose a significant risk to subjects, but the risk is believed to be highest during the Up-dosing Period. The algorithm for missed consecutive doses of IP is as follows:

- Miss 1 to 2 doses in a row – The next dose would be at the current dose level and could be given at home

- Miss 3 to 4 doses in a row – The next dose would be the current dose and would be given under supervision in the CRC
- Miss 5 to 7 doses in a row – Initiate the next dose at approximately 50% of the last tolerated dose (to the nearest feasible available whole dose listed in [Table 2](#) that is \leq 50% of the last tolerated dose). Dosing below 3 mg/day is not allowed. This dose is to be administered under supervision in the CRC. If tolerated, dose escalation may resume with dose increases of 1 dose level occurring no more frequently than weekly and generally no less frequently than every 4 weeks until the subject has returned to the dose level at which the lapse in dosing occurred. If symptoms occur, the dosing guidelines for the up-dosing period apply.
- Missing > 7 consecutive days of dosing due to non-compliance (ie, for any reason other than treatment of an AE or an IP dispensing error) constitutes an individual stopping rule and the subject is to stop taking IP. The subject will be considered an escalation failure non-responder, and will be asked to return to the CRC 14 days following their last dose of IP to undergo an Early Discontinuation Visit ([Section 6.3.6](#)).
- Additionally, excessive missed dosing, defined as 3 consecutive days of missed doses on 3 or more occasions during the Up-dosing Period, for any reason other than treatment of an AE, constitutes an individual stopping rule and the subject is to stop, constitutes an individual stopping rule and the subject is to stop taking IP. The subject will be considered an escalation failure non-responder, and will be asked to return to the CRC 14 days following their last dose of IP to undergo an Early Discontinuation Visit ([Section 6.3.6](#)).

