- Temporarily withholding IP dosing – this may be instituted as treatment for an inter-current AE or to aid the Investigator in determining if a dose level is or is not tolerated, but the duration of withholding IP may not exceed 14 consecutive days, or the subject will be discontinued from the study. The manner in which dosing may resume after withholding dosing of IP depends on the duration for which dosing was withheld.
- If IP has been withheld for 8 to 14 consecutive days as treatment for an AE or due to an IP dispensing error, dosing may be reinitiated at approximately 25% of the last tolerated dose (to the nearest feasible available whole dose listed in [Table 2](#) that is \leq 25% of the last tolerated dose). Dosing below 3 mg/day is not allowed. The reduced dose is to be administered under supervision in the CRC. If tolerated, dose escalation may resume with dose increases of 1 dose level occurring no more frequently than weekly and no less frequently than every 4 weeks until the subject has returned to the dose level at which the lapse in dosing occurred. If symptoms occur, the dosing guidelines for the Up-dosing period apply.
- If IP has been withheld for ≥ 15 consecutive days for any reason, at any point in the study (with the exception of a dosing hiatus instituted for chronic/recurrent GI AEs at or before the 20 mg dose level, as per [Section 6.5.3.2](#)), the subject will be considered an escalation failure non-responder, and will be asked to return to the CRC 14 days following their last dose of IP to undergo an Early Discontinuation Visit ([Section 6.3.6](#)).

No attempt should be made to make up for a missed dose if greater than 6 hours have elapsed since usual time of dosing.

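### The repeated missed-dose rule contradicts itself: three short AE-directed holds end dosing under Protocol 7.9.2 but not under 6.6, and 4.3.1 leaves optional the non-adherence and > 14-day stops that both require

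*Protocol*

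**What the plan says.** Three places in the protocol say when missed doses end treatment.

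- **Section 7.9.2 (Individual Stopping Rules):** "Missing 3 or more consecutive days on 3 occasions is an individual stopping rule". This sentence has no AE exception and names no study period. The two neighbouring rules do carry exceptions: the > 7-day rule excludes AE treatment and dispensing errors, and the 15-day rule excludes the gastrointestinal (GI) hiatus at or before the 20 mg level.
- **Section 6.6 (Missed doses during up-dosing):** the pattern is "3 consecutive days of missed doses on 3 or more occasions during the Up-dosing Period, for any reason other than treatment of an AE". The consequence is compulsory: it "constitutes an individual stopping rule and the subject is to stop taking IP". The same section lets treatment resume after a longer AE hold: if IP is "withheld for 8 to 14 consecutive days as treatment for an AE or due to an IP dispensing error, dosing may be reinitiated". From 15 days onward it requires a stop for any reason, with the GI hiatus excepted.
- **Section 4.3.1 (Criteria for Early Termination):** the relevant list opens "Any subject may be prematurely terminated from additional IP exposures for the following reasons". Item 4, labelled non-adherence, covers "missing > 7 consecutive dosing days on any 1 occasion, or 3 consecutive dosing days on 3 or more occasions during the Up-dosing Period". Item 5 covers medical circumstances "that require missed IP dosing for > 14 consecutive days", again with the GI hiatus excepted.

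AE-related premature discontinuation of dosing is a secondary endpoint (Protocol 9.2.2, SAP 4.2), as is discontinuation for chronic or recurrent GI AEs. SAP 9.1 summarises reasons for discontinuation and lists them as collected on the case report form.

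**The concern.** The rule decides whether a child stays on treatment, and it differs by section. Section 6.6 itself warns that missed doses can carry significant risk, so this is a safety rule.

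It also feeds the analysis in two ways. First, two sites facing the same history could stop one child and continue another, so the count of premature discontinuations depends on which section a site follows. Second, a stop triggered by repeated AE holds has no settled label. Section 4.3.1 item 4 treats the pattern as non-adherence, Section 6.6 calls missed-dose stops escalation failures, and the cause of the missed doses was an AE. The SAP gives no rule for assigning such a stop to the AE-related endpoint.

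**Working it through.** No arithmetic applies, and the plan gives no figure to reproduce. The check sets the three sections side by side for each pattern and reason. An individual stopping rule in 7.9.2 is read as compulsory, because 6.6 uses the same term and attaches the instruction to stop IP.

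| Pattern | 4.3.1 | 6.6 | 7.9.2 | Consistent? |
|---|---|---|---|---|
| (a) Three 3-day holds to treat AEs, in up-dosing | Not clearly reached: item 4 is non-adherence, item 5 needs > 14 days in a row | Exempt; continues | Stops | No |
| (b) Three 3-day misses from non-compliance, in up-dosing | May stop | Must stop | Must stop | No: may versus must |
| (c) One gap > 7 days from non-compliance | May stop | Must stop | Must stop | No: may versus must |
| (d) One AE hold of 8 to 14 days | Not triggered | May restart | Excepted | Yes |
| (e) Medically indicated gap of 15 days or more, not the GI hiatus | May stop | Must stop | Must stop | No: may versus must |

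Row (a) is a direct contradiction. The total missed is 3 × 3 = 9 days, and 7.9.2 ends dosing. A single 14-day AE hold misses more days, yet 7.9.2 allows it to continue, because the > 7-day rule excepts AE treatment and 14 is below 15. This shows only that the section's own exceptions do not fit together; it does not say which outcome is right.

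Rows (b), (c) and (e) differ only in force. Sections 6.6 and 7.9.2 agree with each other; 4.3.1 is the outlier.

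Row (d) is consistent and is not part of the point. Nor is the AE exception to the > 7-day rule, on which 6.6 and 7.9.2 agree.

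Two further wording differences affect the repeated-miss rule:

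1. **Count.** 7.9.2 says at least 3 days on 3 occasions; 6.6 and 4.3.1 say 3 days on at least 3 occasions. Read literally, repeated gaps of 4 days or longer fall under the first more clearly than under the other two.
2. **Period.** 6.6 and 4.3.1 confine the rule to up-dosing; 7.9.2 does not. Section 6.3.5 ends up-dosing at the first 300 mg clinic visit, so later doses fall outside it. That stretch is usually 2 weeks but can be longer, since subjects may remain on blinded 300 mg dosing while follow-on protocols are activated (Protocol 6.4, SAP 7.1).

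**The case against.** The strongest reply is that the protocol shows which section governs. The dose-adjustment text in 6.5.5.2 treats doses withheld for an AE as a special category of missed doses and points to 6.6. On that view 7.9.2 is a summary that dropped one clause, and a reader who knows 6.6 would supply it. This reading is available, but the text does not compel it. Section 7.9.2 refers to 6.5.3.2 and never to 6.6, these sections state no order of precedence, and 7.9.2 gives exceptions for its other two rules. A site could reasonably take the missing exception as intended.

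On may versus must, the reply is that 4.3.1 uses *may* loosely: a later list there says a subject may be discontinued if the subject dies. A general permissive list can sit beside specific compulsory rules. This has some force and makes it the weaker half of the point. But the list immediately before uses *will*, so the section does separate compulsory from discretionary stops and places missed dosing among the latter.

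It is also fair that the period difference has limited reach, and that part of the classification can be recovered. SAP 9.5 lists the reason for each missed home dose and excludes investigator-ordered misses from planned dosing days, and SAP 9.8.1 tabulates events leading to discontinuation of study product. That helps to label a stop after the fact. It does not undo a stop that another site would not have made.

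A reader might go further and infer that 7.9.2 has no exceptions at all, or that any AE hold may or may not end treatment. Row (d) and the exceptions quoted from 7.9.2 rule that out.

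**Conclusion.** The repeated missed-dose rule is wrong as written. For three short AE-directed holds in up-dosing, 7.9.2 and 6.6 give opposite instructions. For non-adherence and for medically indicated gaps beyond 14 days, 4.3.1 is discretionary where the other two sections are compulsory, apart from the GI hiatus.

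The effect on the results cannot be sized. No passage gives the frequency of repeated holds, overall or by arm. A reader might infer a bias against AR101 from ARC001, where 4 of 29 AR101 subjects (14%) and no placebo subject discontinued for an AE (Protocol 1.2.1). Those figures count discontinuations, not holds, and come from a small study that also had a maintenance period. Sites here are blinded, and Protocol Section 9 plans no hypothesis test between groups. What can be said is that the conflict may change who stops dosing and whether the stop counts as AE-related. The conclusion rests on the text alone and on reading a stopping rule as compulsory.

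**What to change.** Reconcile Protocol Sections 4.3.1, 6.6 and 7.9.2 into one missed-dose rule, state it once, and have the other places refer to it. The wording must settle four things: whether the stop is compulsory or discretionary, whether and how AE-related misses are excepted, which study periods it covers, and the count of days and occasions. The content of each is for the sponsor's clinical team.

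In the SAP 9.1 disposition summary, show stops triggered by the missed-dose rule separately, divided by whether the missed doses were AE-related, and state which of these count towards the AE-related discontinuation endpoint.

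The cost is a protocol clarification and one added split in a table; the reasons for missed home doses are already collected in the diary. If dosing has already finished, the clarification can no longer change conduct, but the split can still be made and the report can state how sites applied the rule.
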